5.2.6.2.2 AE reporting to the sponsor and timelines

The investigator must report SAEs, AESIs, and non-serious AEs which are relevant for the reported SAE or AESI, on the BI SAE form via fax immediately (within 24 hours) to the sponsor's unique entry point (country specific contact details will be provided in the ISF). The same timeline applies if follow-up information becomes available. In specific occasions, the investigator could inform the sponsor upfront via telephone. This does not replace the requirement to complete and fax the BI SAE form.

With receipt of any further information to these events, a follow-up SAE form has to be provided. For follow-up information the same rules and timeline apply as for initial information. All (S)AEs, including those persisting after individual patient's end of trial must be followed up until they have resolved, have been assessed as "chronic" or "stable", or no further information can be obtained.

5.2.6.2.3 Pregnancy

In rare cases, pregnancy might occur in a clinical trial. Once a patient has been enrolled in the clinical trial and has taken trial medication, the investigator must report any drug exposure during pregnancy in a trial participant immediately (within 24 hours) by means of Part A of the Pregnancy Monitoring Form to the sponsor's unique entry point.

Similarly, potential drug exposure during pregnancy must be reported if a partner of a male trial participant becomes pregnant. This requires written consent of the pregnant partner. Reporting and consenting must be in line with local regulations. The ISF will contain the trial specific information and consent for the pregnant partner.

The outcome of the pregnancy associated with the drug exposure during pregnancy must be followed up and reported to the sponsor's unique entry point on the Pregnancy Monitoring Form for Clinical Studies (Part B).

The ISF will contain the Pregnancy Monitoring Form for Clinical Studies (Part A and B).

As pregnancy itself is not to be reported as an AE, in the absence of an accompanying SAE and/or AESI, only the Pregnancy Monitoring Form for Clinical Studies and not the SAE form is to be completed. If there is an SAE and/or AESI associated with the pregnancy an SAE form must be completed in addition.

5.2.6.2.4 Exemptions to SAE reporting

No exemptions are defined.

Proprietary confidential information © 2021 Boehringer Ingelheim International GmbH or one or more of its affiliated companies

5.3 DRUG CONCENTRATION MEASUREMENTS AND PHARMACOKINETICS

5.3.1 Assessment of pharmacokinetics

For the assessment of pharmacokinetics, blood samples and sputum will be collected at the time points indicated in the Flow Chart. The actual sampling times will be recorded and used for determination of pharmacokinetic parameters.

5.3.2 Methods of sample collection

5.3.2.1 Plasma sampling for pharmacokinetic analysis

The planned PK analyses of BI 1323495 and its metabolite CD 7545 will require blood sampling at the time points indicated in the Flow Chart. Correct, complete and legible documentation of drug administrations and blood sampling times as well as adequate handling and identification of PK samples are mandatory to obtain data of adequate quality for the PK analysis.

In order to allow the sample identification, the sample tube labels should list at a minimum the following information: BI trial number, patient number, visit, matrix and planned sampling time.

After completion of the trial, the plasma samples may be used for further methodological investigations (e.g. for stability testing or assessment of metabolites). However, only data related to the analyte and/or its metabolite(s) will be generated by these additional investigations. The study samples will be discarded after completion of the additional investigations but not later than 5 years after the CTR is archived.

5.3.2.2 Sputum sampling for pharmacokinetic analysis

Spontaneous sputum will be collected as indicated in the Flow Chart. In case no adequate sputum sample is produced spontaneously, induction of sputum with isotonic, or subsequently hypertonic saline is mandatory. If sputum samples do not meet the quality criteria as directly assessed at the site, re-sampling at the next day is generally possible.

Whether the BI 1323495 and CD 7545 concentrations in sputum will be measured depends on the amount of sputum expectorated at the clinical sites as the measurements for the secondary endpoints in sputum take precedence over PK analysis (further details will be provided in the lab manual). Hence, it might be that not at all visits with sputum collection PK samples are taken.

Correct, complete and legible documentation of drug administrations and sputum sampling times as well as adequate handling and identification of sputum PK samples are mandatory to obtain data of adequate quality for the sputum PK analysis.

Boehringer Ingelheim		22 Apr 2021
BI Trial No.: 1405-0008		_
c31693972-02	Clinical Trial Protocol	Page 71 of 111

In order to allow the sputum sample identification, the sample tube labels should list at a minimum the following information: BI trial number, patient number, visit, matrix and planned sampling time.

After completion of the trial, the sputum samples may be used for further methodological investigations (e.g. for stability testing or assessment of metabolites). However, only data related to the analyte and/or its metabolite(s) will be generated by these additional investigations.

The left over sputum samples will be transferred to the biobank after completion of these analysis but no later than 5 years after signature of the CTR (see Section 5.5).

1693972-02Clinical Trial ProtocolPage 72 of 111Proprietary confidential information © 2021 Boehringer Ingelheim International GmbH or one or more of its affiliated companies
Page 73 of 111

Proprietary confidential information © 2021 Boehringer Ingelheim International GmbH or one or more of its affiliated companies

5.5 **BIOBANKING**

Participation in biobanking is voluntary and not a prerequisite for participation in the trial. Biobanking will only occur after a separate biobanking informed consent has been given in accordance with local ethical and regulatory requirements.

5.5.1 Methods and timing of sample collection

Approximately 60 mL blood will be drawn per patient for serum banking and spot urine will be collected at timepoints indicated in the Flow Chart.

In addition left over sputum volume (see Section 5.3.2.2 and 5.4) will be used for banking purposes.

Detailed instructions on sampling, preparation, processing, shipment and storage are provided in the laboratory manual. For sampling timepoints see Flow Chart.

5.6 OTHER ASSESSMENTS

5.7 APPROPRIATENESS OF MEASUREMENTS

All measurements performed during this trial are standard measurements and will be performed in order to monitor subjects' safety and to determine pharmacokinetic parameters

Boehringer Ingelheim		22 Apr 2021
BI Trial No.: 1405-0008		_
c31693972-02	Clinical Trial Protocol	Page 74 of 111

in an appropriate way. The scheduled measurements will allow monitoring of changes in vital signs, standard laboratory values, and ECG parameters that might occur as a result of administration of trial medication. The safety assessments are standard, are accepted for evaluation of safety and tolerability of an orally administered drug, and are widely used in clinical trials. The pharmacokinetic parameters and measurements outlined in Section 5.3 are generally used assessments of drug exposure.

Page 75 of 111

Proprietary confidential information © 2021 Boehringer Ingelheim International GmbH or one or more of its affiliated companies

6. INVESTIGATIONAL PLAN

6.1 **VISIT SCHEDULE**

The study scheme, including all visits, is shown in Section 3.1, Figure 3.1: 1.

Screening Visit 1 will be done at least 7 days prior to Baseline (BSL) Visit 2a. During BSL (V2a, V2b, V3), there will be a minimum of two and up to three valid sputum samples within indicated timeframes. The End of Treatment (EoT) Visit 10 will be done 12 weeks after randomisation. Prior to EoT, during V9 and V10, i.e. Day 78-82 and EoT, two to three valid sputum samples will be obtained within seven days.

The acceptable time windows for screening, for measurements and assessments are provided in the main Flow Chart and are also described in the Section 6.2 below.

The Sample and Assessment Flow Chart provides sputum, PK and PD details for timing of sampling as well as conduct of lung function meassurements and questionnaires. Planned blood sampling times should be adhered to as closely as possible.

The acceptable deviation from the scheduled time for vital signs, ECG, PK and laboratory tests will be \pm 15 min. The exact times of trial visit assessments and measurements outside the permitted time windows will be documented in the eCRF.

If a patient misses an appointment, it will be rescheduled if possible. The relevance of measurements outside the permitted time windows will be assessed no later than at the Report Planning Meeting.

In exceptional circumstances during COVID-19 pandemic, when it is impossible to conduct study visits at the study site, study visits may be performed at patient's home or remotely (via telephone and/or internet based means of communication). Visits may also be performed as a hybrid of home and remote visit. All home/remote visits need to be discussed with and authorised by the sponsor's trial team. The trial team's decision will be based on a thorough benefit-risk evaluation.

The procedures performed during a home/remote visit may be adjusted as compared to a regular visit, as detailed in Appendix 10.4

All COVID-19 related deviations from the original schedule of visits and procedures will be documented and the implications considered for the analysis of the trial data.

6.2 DETAILS OF TRIAL PROCEDURES AT SELECTED VISITS

6.2.1 Screening and run-in period

Screening Period

Boehringer Ingelheim		22 Apr 2021
BI Trial No.: 1405-0008		
c31693972-02	Clinical Trial Protocol	Page 76 of 111

After having been informed about the trial, all subjects will provide written informed consent in accordance with GCP and local legislation prior to enrolment in the study. At screening, the medical examination will include demographics, height and body weight, smoking and alcohol use, relevant medical history and concomitant therapy, review of inclusion and exclusion criteria, review of vital signs (BP, PR, aural body temperature), 12-lead ECG, pregnancy testing, laboratory tests (including UGT2B17 genotyping), sputum collection, lung function and a physical examination. For information regarding physical examination, vital signs, laboratory tests and ECG refer to Sections 5.2.1, 5.2.2, 5.2.3 and 5.2.4.

Genotyping for UGT2B17 will be performed in all trial patients (for details, see Section 5.4). The Screening Visit 1 can cover a period of up to 4 weeks, e.g. to wait for laboratory results, or if washout of certain restricted medication is required (see Section 4.2.2.1).

During the baseline period (Visits 2a, b and Visit 3 before treatment), patients have to donate two to three valid sputum samples.

6.2.2 Treatment period

After Visit 3 with first drug administration, patients will visit the site after 2, 4, 8, 11 and 12 weeks. Visit 4 after 1 week of treatment start will be conducted as a phone call with the patient. At Visit 7, 6 weeks after treatment start, the patient will be contacted via phone, and blood collection for safety laboratory will be done via a local lab or a flying nurse.

Following first drug administration in Part A, the evening and the morning dose should be taken with a 12 h time interval (e.g. 20:00 h and 08:00 h) approximately at the same time each day during the treatment phase, within a time window of +/- 1 hour. In Part B, the oncedaily dose should be taken approximately at the same time each morning during the treatment phase. Drug should be taken 15-30 min after food intake including a fat component (like yogurt, milk, cheese or sausage). As an exemption, at Visit 3 and Visit 6, drug administration will happen at the site outside the normal schedule. Patients will then go back to their usual evening/morning interval (Part A) or once-daily interval (Part B), respectively. On PK day at Visit 6, patients will stay at site for the reason of medical surveillance.

The provided time according the Sample and Assessment Flow Chart is approximate; i.e. a deviation from the scheduled time of the day of \pm 120 minutes is acceptable. The relative time deviations from time of administration should be kept as minimal as possible and should be below \pm 15 minutes for PK measurements on PK days. The exact time of sample collection should be collected in electronic Case Report Form (eCRF). Patient questionnaires will be completed by the patient alone in a quite room.

Sputum collection should occur during a 2h timeframe with active breathing techniques or equivalent manouvres, if necessary. Study nurse / physiotherapist needs to be available to support patient in performing active cycle of breathing technique in case of difficulties producing sputum. Next step will be Oscillating Positive Expiratory Pressure (OPEP), if despite breathing technique still no sputum is being produced. Patients who produce an adequate sputum sample do not have to undergo these supportive measures. In case no

Boehringer Ingelheim		22 Apr 2021
BI Trial No.: 1405-0008		
c31693972-02	Clinical Trial Protocol	Page 77 of 111

adequate sputum sample is produced spontaneously, induction of sputum with isotonic, or subsequently hypertonic saline is mandatory. If sputum samples do not meet the quality criteria as directly assessed at the site, re-sampling at the next day is generally possible. An instruction on sputum handling will be provided to the site in the ISF.

If treated with bronchodilators, wash-out of 24 hours for qd long acting, 12 hours for bid long acting, and 8 hours for short acting bronchodilators should be observed before pulmonary function tests.

The safety measurements performed during the treatment period are specified in Section 5.2 of this protocol and in the Flow Chart. For details on times of all other trial procedures, refer to the Flow Chart.

AEs and concomitant therapy will be assessed continuously from screening until the end ofstudy.

6.2.3 Follow-up period and trial completion

End of Study assessments must be conducted at least 7 days after the last trial drug intake, i.e. after the REP for BI 1323495.

For AE assessment, laboratory tests, recording of ECG and vital signs, sputum collection, lung function and physical examination during the End of Study Visit, see Section 5.2. Patients who discontinue treatment before the end of the planned treatment period should also undergo the EoT Visit, at least 7 days after the last trial drug intake.

All abnormal values (including laboratory parameters) that are assessed as clinically relevant by the investigator will be monitored using the appropriate tests until a return to a medically acceptable level is achieved. (S)AEs persisting after a subject's EoT Visit must be followed up until they have resolved, have been sufficiently characterised, or no further information can be obtained.

Male subjects with 'women of childbearing potential' (WOCBP) partner will be reminded to use male contraception (condom or sexual abstinence) during the trial until 30 days after the last administration of trial medication.

Page 78 of 111

Proprietary confidential information © 2021 Boehringer Ingelheim International GmbH or one or more of its affiliated companies

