Zymosan stimulation in whole blood			X	X		X	X		X			X	X
Cotinine test			Χ	Х		X	X		Χ			X	X
Serum banking sample (optional) ⁹			X	X		X	X		X			X	X
Urine banking sample (otional) ⁹			X										
Pulmonary Function Test (PFT) ¹⁰	X		X			X			X			X	X
All AEs/SAEs/AESIs ¹¹	X	Χ	Χ	Χ	Χ	X	X	X	Χ	Χ	Χ	X	X
Compliance check (medication)						X	X		X			X	
Completion of patient participation													X

Boehringer Ingelheim		22 Apr 2021
BI Trial No.: 1405-0008		
c31693972-02	Clinical Trial Protocol	Page 7 of 111
	Proprietary confidential information © 2021 Boehringer Ingelheim International GmbH or one or more of its affiliated companies	
1. Informed consent need	s to be signed before any procedure related to this trial is performed (before or at Visit 1).	

- 2. Timing of sampling and assessments: see Sample and Assessment Flow Chart.
- 3. Day of Randomisation / Day of first intake of randomised medication.
- 4. Patients who discontinue trial treatment prematurely should undergo an early End of Treatment (EoT) visit as soon as possible (study procedures will be the same as for Visit 10 (EoT) except no treatment will be administered). Follow up Visit (End of Study (EoS)) will be 14 days +/- 4 days thereafter.
- 5. Serum pregnancy test is to be performed if urine test positive and no Investigational Medicinal Product (IMP) to be given until negative result confirmed.
- 6. Following first drug administration in Part A, evening and morning dose should be taken with a 12 h time interval (e.g. 20:00 h and 08:00 h) approximately at the same time each day during the treatment phase, within a time window of +/- 1 hour. In Part B, the once-daily dose should be taken approximately at the same time each morning during the treatment phase. Drug should be taken 15-30 min after food intake including a fat component (like yogurt, milk, cheese or sausage). As an exemption, at Visit 3 and Visit 6, drug administration will happen at the site outside the normal schedule. Patients will then go back to their usual evening/morning interval (Part A) or once-daily interval (Part B), respectively. At Visit 3, patient will receive a reserve kit in case medication gets lost or the patients comes back to the next visit after more than 2 weeks. The morning drug administration date/time is collected on the eCRF for all Visits 3 to 10 (except Visit 4).
- 7.
- 8. Sputum containers for 24h sputum collection will be provided to the patient at Visit 2b, Visit 5 and Visit 9b.

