- 6. If treated with bronchodilators, wash-out of 24 hours for qd long acting, 12 hours for bid long acting, and 8 hours for short acting bronchodilators should be observed before pulmonary function tests.
- 7. Including urine drug screening and alcohol breath test
- 8. Collection of biobanking samples is optional. Participating patients are required to give informed consent specifically for biobanking. Samples will be stored at a biobanking facility for future research.

22 Apr 2021

Boehringer Ingelheim		22 Apr 2021
BI Trial No.: 1405-0008		
c31693972-02	Clinical Trial Protocol	Page 11 of 111
	Proprietary confidential information © 2021 Boehringer Ingelheim International GmbH or one or more of its affiliated companies	

9. Discharge is not mandatory and always at discretion of the investigator. Patient in-house stay may be extended at any time if deemed clinically necessary. The subjects are only allowed to leave the trial site after formal assessment and confirmation of their fitness by the investigator or designee.

10. Following first drug administration in Part A, evening and morning dose should be taken with a 12 h time interval (e.g. 20:00 h and 08:00 h) approximately at the same time each day during the treatment phase, within a time window of +/- 1 hour. In Part B, the once-daily dose should be taken approximately at the same time each morning during the treatment phase. Drug should be taken 15-30 min after food intake including a fat component (like yogurt, milk, cheese or sausage). As an exemption, at Visit 3 and Visit 6, drug administration will happen at the site outside the normal schedule. Patients will then go back to their usual evening/morning interval (Part A) or once-daily interval (Part B), respectively.

11. At V11, only Vital Signs need to be assessed

Page 12 of 111

Proprietary confidential information © 2021 Boehringer Ingelheim International GmbH or one or more of its affiliated companies

TABLE OF CONTENTS

TITLE F	PAGE	1
CLINIC	CAL TRIAL PROTOCOL SYNOPSIS	3
MAIN F	LOW CHART	5
SAMPL	E AND ASSESSMENT FLOW CHART	8
TABLE	OF CONTENTS	12
ABBRE	VIATIONS	16
1.	INTRODUCTION	21
1.1	MEDICAL BACKGROUND	
1.2	DRUG PROFILE	21
1.2.1	Mode of action	
1.2.2	Data from non-clinical and toxicology studies	
1.2.2.1	Non-clinical pharmacology	
1.2.2.2	Non-clinical pharmacokinetics	23
1.2.2.3	Drug interactions	23
1.2.2.4	Toxicology	24
1.2.3	Data from clinical studies	24
1.2.3.1	Clinical pharmacokinetics	25
1.2.3.2	Clinical Pharmacodynamics	

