3.3.4.1 Discontinuation of trial treatment

An individual patient will discontinue trial treatment if:

- The patient wants to discontinue trial treatment, without the need to justify the decision.
- The patient has repeatedly shown to be non-compliant with important trial procedures and, in the opinion of both, the investigator and sponsor representative, is not willing or able to adhere to the trial requirements in the future.
- The patient can no longer receive trial treatment for medical reasons (such as surgery, adverse events, other diseases, or pregnancy). The subject shows an elevation of AST and/or ALT ≥3-fold upper limit of normal (ULN) combined with an elevation of total bilirubin ≥2-fold ULN (measured in the same blood sample) and/or needs to be followed up according to the 'DILI checklist' provided in the ISF.
- The subject experiences an infection with SARS-CoV-2 (as confirmed by PCR Test, see Section 5.2.3) or an infection other than pulmonary exacerbation which requires systemic antibiotic treatment. In case a patient needs to take concomitant medication that interferes

with the investigational medicinal product or other trial treatment (see Section 4.2.2), it will be decided on a case-by-case basis after consultation with the Sponsor whether or not discontinuation of trial treatment is required.

If new efficacy/safety information becomes available, Boehringer Ingelheim will review the benefit-risk-assessment and, if needed, pause or discontinue the trial treatment for all patients or take any other appropriate action to guarantee the safety of the trial patients.

Boehringer Ingelheim		22 Apr 2021
BI Trial No.: 1405-0008		
c31693972-02	Clinical Trial Protocol	Page 52 of 111

Even if the trial treatment is discontinued, the patients remain in the trial and, given their agreement, will undergo the procedures for early treatment discontinuation and follow-up as outlined in the Flow Chart and Section 6.2.3.

Additional patients may be recruited, if early treatment discontinuation is due to non-safety related reasons (e.g. unable to continue protocol defined visits due to personal reason), or due to COVID-19 given the prevalence of the coronavirus in the community. In all cases, recruitment of additional patients should only occur if the patient discontinued treatment prior to week 12, and must first be discussed and agreed upon with the sponsor.

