# 6. GENERAL ANALYSIS DEFINITIONS

#### 6.1 TREATMENTS

For basic study information on treatments to be administered in each trial part, assignment of treatment groups, and selection of doses, cf. Section 4 of the CTP.

Placebo patients will be analysed according to their respective study part, i.e. posology. If deemed appropriate the assessment of a pooled placebo group will be added.

Analysis phases for statistical analysis of AEs, safety laboratory data, vital signs and biomarkers are defined for each patient as described in Table 6.1: 1.

Table 6.1: 1 Analysis phases for statistical analysis of AEs, and actual treatment for analysis of laboratory data and vital signs

Study analysis			
phase	Label	Start (included)	End (excluded)
Screening	Screening	Date of informed consent at 12 a.m.	Date/time of first administration of study drug
On-treatment	Placebo bid Placebo qd BI 30mg bid BI 150mg qd respectively	Date/time of first administration of study drug	12:00 a.m. on day after last administration of study drug + REP (7 days) or 12:00 a.m. on day after last contact date (whichever occurs first)
Follow-up 	Follow-up	12:00 a.m. on day after last administration of study drug + REP (7 days)	12:00 a.m. on day after last contact date

<sup>1This phase exists only in those patients who have last contact 7 or more days after last trial drug administration.

AE displays in CTR Section 15.3, Appendix 16.1.13.1.8.2 and Appendix 16.1.13.1.8.3 will present results for the on-treatment phase only.

Safety laboratory data, vital signs and clinical assessment data will be analysed based on dose groups (not on analysis phases defined above), with clear differentiation between baseline (refer to Section 6.7) and on-treatment measurements. Measurements will be considered ontreatment, if they were taken within the on-treatment phases as defined in Table 6.1: 1.

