# 6.7 BASELINE, TIME WINDOWS AND CALCULATED VISITS

For all parameters, except for biomarkers, baseline is defined as the last non-missing value prior to first administration of the trial treatment. In case of planned multiple measurements of biomarkers within the run-in period prior to first drug administration (e.g. at Visit 2a, 2b or 3), the following will apply:

Measurements taken after first administration of trial treatment will be considered either onor off-treatment values based on the definition in Table 6.1: 1, and will be assigned to visits for statistical analysis, if applicable, as defined below.

Analysis of AE data (including findings in 12-lead ECG assessments or physical examinations), potentially clinically significant abnormal laboratory values, concomitant medication or non-drug therapies will not be based on visits. Frequency tables for AE data will be using on-treatment data and categorized based on their occurring/starting dates. Therefore, no assignment to time windows will be necessary for such data.

Analysis day is calculated as follows:

If assessment date and time is prior to the date and time of first study drug intake: Date of assessment – date of first study drug intake

If assessment date and time is greater or equal to the date and time of first study drug intake: Date of assessment – date of first study drug intake +1 day

Analysis visit windows for other assessments during the study are given in the following tables. The date of the first drug intake will be used as study day 1 for the time windowing (including planned first drug administration visit V3 and repeated V3). If more than one value is available within one time window the one which is closest to the planned time/day is used for analysis. In case two values are equidistant from the planned time/day, then the last one will be picked.

TSAP for BI Trial No: 1405-0008 Page 16 of 25

Proprietary confidential information © 2022 Boehringer Ingelheim International GmbH or one or more of its affiliated companies

Time windows for assignment of safety assessment – laboratory Table 6.7: 2

			Time window [days]		
Visit			Window	Start	End
number	Visit label	Planned	per CTP	(analysis)	(analysis)
(CTP)	(analysis)	Day			
V1	Screening	-27	± 14	All pre-baselin	e measurements
V3	Baseline	1	$\pm 0$	NA	Date/time of first
					administration of
					study drug
V5	Week 2	15	$\pm 3$	Start of on-	22
				treatment phase	
				as defined in	
				table 6.1.1	

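### For early stoppers, protocol 6.2.3 contradicts the Flow Chart on End of Treatment timing, and the SAP's 7-day on-treatment rule is too wide for NE biomarkers

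*Protocol*

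**What the plan says.** **Visit timing (protocol).** Main Flow Chart footnote 4: "Patients who discontinue trial treatment prematurely should undergo an early End of Treatment (EoT) visit as soon as possible". It continues: "Follow up Visit (End of Study (EoS)) will be 14 days +/- 4 days thereafter". It sets no upper limit on the early EoT visit. Section 6.2.3 opens with a 7-day minimum after the last dose for End of Study, tied to the Residual Effect Period (REP). It then says that patients who stop early "should also undergo the EoT Visit, at least 7 days after the last trial drug intake". Section 3.3.4.1 says that these patients "will undergo the procedures for early treatment discontinuation and follow-up as outlined in the" Flow Chart and Section 6.2.3. It does not say which prevails.

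**ECG.** The Main Flow Chart schedules no ECG after Visit 10. On the combined ECG and vital-signs column, footnote 11 of the Sample and Assessment Flow Chart says: "At V11, only Vital Signs need to be assessed". Section 6.2.3 does mention ECG at End of Study, but the charts schedule none.

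**Analysis phase (SAP).** Section 6.1: "Analysis phases for statistical analysis of AEs, safety laboratory data, vital signs and biomarkers are defined for each patient". In Table 6.1: 1 the on-treatment phase runs up to, but not including, midnight at the start of the day after last dose plus 7 days, or the day after last contact if that is earlier. Section 6.7 adds: "Measurements taken after first administration of trial treatment will be considered either onor off-treatment values based on the definition in" that table.

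**Target of the secondary objective.** Protocol 2.1.1 frames it for patients who stay on treatment for the full 12 weeks without prohibited medication. Section 3.2 expects NE inhibition to have fully reversed within the 2-week follow-up.

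**The concern.** A site cannot follow both timing rules. A visit on days 1 to 6 after the last dose breaches 6.2.3, and a deliberate one-week wait breaches footnote 4. A site that follows 6.2.3 postpones the scheduled EoT laboratory tests, vital signs and ECG, even for a patient who stopped because of an adverse event. That ECG is the last one in the charts.

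The analysis problem is separate. A 7-day residual-effect window is sensible for attributing adverse events. For a reversible inhibitor it is a poor definition of being on drug, because a sample taken on day 4 or day 7 is labelled the same as one taken at trough. The visible exclusions for NE data cover recent exacerbations (protocol 7.2.3), late sputum processing and restricted medication (SAP 6.6.2). None covers a sample taken after dosing has stopped. At stake are the by-visit summaries of NE activity, change and percent change in arms of 9 and 18 patients.

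**Working it through.** **1. The plan's own figure.** Protocol 1.2.4 gives an REP of 7 days from 5 half-lives of 30 h: 5 × 30 = 150 h = 6.25 days, which is 7 when rounded up. At day 7, 168/30 = 5.6 half-lives have passed and 0.5^5.6 = 2.1% of the drug remains.

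**2. The two timing rules against the SAP phase** (day 0 = last dose):

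| Early EoT on day | Protocol 6.2.3 | SAP Table 6.1: 1 |
|---|---|---|
| 1 to 6 | breached | on-treatment |
| 7 | met | on-treatment |
| 8 or later | met | Follow-up |

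A visit that obeys 6.2.3 is therefore on-treatment on one day only, when little drug is left. From day 8 the patient has no on-treatment EoT value.

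**3. End of Study timing.** With early EoT on day 1 or 2, footnote 4 puts EoS between day 1 + 10 = 11 and day 2 + 18 = 20, beyond the 7-day REP. With 6.2.3 as written, EoS falls no earlier than day 7 + 10 = 17.

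**4. How far inhibition falls off drug (blood model, illustration only).** Inputs from protocol 1.2.3.2: IC50 3.6 nM; median trough inhibition 91.8% (30 mg bid) and 93.1% (120 mg qd, used as a proxy for 150 mg qd). Inhibition = C/(C + 3.6). Check: this gives IC90 = 3.6 × 0.90/0.10 = 32.4 and IC95 = 3.6 × 0.95/0.05 = 68.4 nM, against 33 and 69 stated.

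Trough concentration: 3.6 × 0.918/0.082 = 40.3 nM at 12 h (bid); 3.6 × 0.931/0.069 = 48.6 nM at 24 h (qd). Decay is log-linear from there. The 30 h half-life is the 600 mg single-dose value, which protocol 1.2.3.1 reports as longer than in the other dose groups. No figure is given for those groups, so 15 h is an assumption.

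The shift in the arm mean from one such patient is (trough − value)/n, taking the median trough as the mean of the others. Each cell shows 30 h / 15 h.

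| Day | 30 mg bid, % inhibition | Shift, 1 of 9 | qd proxy, % inhibition | Shift, 1 of 18 |
|---|---|---|---|---|
| 1 | 89.5 / 86.5 | 0.3 / 0.6 | 93.1 / 93.1 | 0 / 0 |
| 2 | 83.0 / 68.0 | 1.0 / 2.6 | 88.6 / 81.7 | 0.3 / 0.6 |
| 4 | 61.6 / 18.8 | 3.4 / 8.1 | 71.9 / 32.6 | 1.2 / 3.4 |
| 7 | 23.3 / 0.8 | 7.6 / 10.1 | 32.6 / 1.7 | 3.4 / 5.1 |

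A half-life of 10 h would give 48.0% (bid) and 71.9% (qd proxy) at day 2. The shifts are then (91.8 − 48.0)/9 = 4.9 and (93.1 − 71.9)/18 = 1.2 points.

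**5. Who could reach the Week 12/EoT summary.** The biomarker window is not in this copy. If it matched the laboratory and spirometry windows, which start at day 71, a day-7 sample would count for last doses from day 71 − 7 = 64 onward. Earlier stoppers would map to earlier visits. Sputum values would be averaged with any valid V9a or V9b sample. Blood has no other scheduled PD sample between Visit 8 (day 57) and Visit 10 (day 84).

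**The case against.** **The 6.2.3 sentence is a slip.** This is likely. The section concerns follow-up and trial completion, and it opens with the same 7-day minimum for EoS. Its later rule on events persisting after EoT matches one in 5.2.6.2.2 that refers to the patient's end of trial. Read as EoS, the sentence agrees with footnote 4. That supports the correction, but sites still have two conflicting instructions.

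**Safety.** A reader might infer that patients who stop for an adverse event go unchecked for a week. The protocol does not support that. Adverse events are assessed continuously (6.2.2), additional ECGs may be recorded (5.2.4), symptoms of hepatic injury call for unscheduled bloods (5.2.6.1.4), and clinically relevant abnormal values are followed (6.2.3). Only the scheduled check is delayed.

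**Unseen text.** A reader might also infer that off-drug values will bias the Week 12 sputum endpoint. The biomarker baseline and window rules, SAP Section 9.1 and the protocol-deviation (DV) specifications are not in this copy. The absence of a visible exclusion does not prove that there is none.

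**The numbers are not on the endpoint.** Correct. They are percent inhibition in healthy-volunteer blood, whereas the endpoints are changes in NE activity in patients. Sputum kinetics are unknown. The largest shift needs a visit on exactly day 7.

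**The day-8 value is not really lost.** Also fair. It is off drug, so Follow-up is the right class, and it is still listed. What is lost is the chance to sample near the last dose.

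**Conclusion.** The conflict between 6.2.3 and footnote 4 stands on current text and needs correcting, probably as an EoT/EoS slip. Its direct effects are a delayed scheduled safety check and, from day 8, no on-treatment EoT value.

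The biomarker point is secondary. As visible, SAP 6.1 and 6.7 let an NE sample several days off drug count as on-treatment, which does not fit the condition in protocol 2.1.1. Under prompt visits the effect is small: at day 2 the model gives 1.0 to 2.6 points for one patient of 9 and 0.3 to 0.6 for one of 18. It grows as the visit slips toward day 7. These sizes rest on the blood model, a half-life of 15 to 30 h and the qd proxy.

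The documents do not support a claim that the trial's NE results are materially biased. Only early stoppers are affected and their number is not given. The trial is exploratory, and the primary endpoint, completers and patient-level maximum inhibition are unaffected.

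**What to change.** **Protocol 6.2.3:** apply the 7-day minimum to the End of Study visit only. Keep the early EoT visit as soon as possible after the last dose, with a target such as within 2 days. A visit that misses the target is still held for safety.

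**SAP 6.1 and 6.7:** keep last dose plus 7 days for adverse events. For NE biomarkers, end the on-treatment phase shortly after the last dose and list later values separately, unless the biomarker window or DV specifications already do this. The limit is a judgement, from one dosing interval (12 h bid, 24 h qd) to about 2 days. The shorter end is cleaner, since modelled inhibition for 30 mg bid has already fallen to 68 to 83% at day 2. The longer end keeps more samples.

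**Cost:** one sentence in a protocol amendment and one SAP rule, using the last-dose date that Table 6.1: 1 already needs. No visits or patients are added. A few early-stopper samples move from summaries to listings.
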